8.1.2 Efficacy Assessments

For all baseline assessments and follow-up visits, refer to the Schedule of Assessments (SOA) for procedure to be done, and details below for each assessment.

8.1.2.1 Measures of clinical support, limitations and infection control

The subject's clinical status, as measured by the ordinal scale, will be captured at randomization and Day 2 through Day 29 (+ 6-day window) while hospitalized or day after death whichever comes first. The ordinal scale will also be captured on the day after discharge from the hospital. This will be done so that discharge and death are accurately recorded and captured in the eClinical system. For subjects who received oxygen by nasal cannula or CPAP ventilatory support at night at home prior to having COVID-19, sites should assign a recovery ordinal scale score of 1 or 2 when discharged to home after recovery. The assignment of category 1 versus category 2 will depend on whether they have new or increased physical limitations post-COVID-19 and/or if they have new or increased home oxygen requirement compared with the baseline, pre-COVID-19 time period.

It is important to capture all deaths that occur during the study as this is one of the outcomes of the study. Death is a category on the ordinal scale. If a subject dies during the study, an ordinal scale assessment should be completed for the day after death because the ordinal scale captures the worst clinical assessment for the previous day. If the site is aware of a subject death after the day 29 visit but within the window of the Day 29 study visit (i.e., Day 29 + 6-day window), complete an ordinal scale assessment on the day after death.

After a subject is discharged, clinical status as measured by ordinal scale will be collected on remaining outpatient visits (Day 15, 22, 29, and 60). The ordinal scale can be assessed at an in-person clinic visit or by phone, home visit or remote telehealth procedure as per institutional standards if an in-person visit at the clinical trial site is not possible.

Ordinal scale is an assessment of death or the highest ventilatory support received in the last 24-hour period and therefore can be assessed at any time on the subsequent day. The following measures are recorded for the ordinal scale. See MOP for more detailed description of ventilatory devices in each category:

- Hospitalization.
- Oxygen requirement.

- Non-invasive ventilation requirement (CPAP, BiPAP).
- High flow oxygen requirement.
- Invasive mechanical ventilation (via endotracheal tube or tracheostomy tube) requirement.
- ECMO requirement.
- Ongoing medical care preventing hospital discharge (COVID-19 related or other medical conditions).
- Limitations of physical activity (self-assessed and reported as new or increased limitations as compared to status prior to the onset of COVID-19).
- Isolated for infection control purposes.

8.1.2.2 Ordinal Scale

The ordinal scale is used as the primary clinical assessment of subjects during the study.

The scale used in this study is as follows (from worst to best):

Category 8: Death;

Category 7: Hospitalized, on invasive mechanical ventilation or ECMO;

Category 6: Hospitalized, on non-invasive ventilation or high flow oxygen devices;

Category 5: Hospitalized, requiring supplemental oxygen;

Category 4: Hospitalized, not requiring supplemental oxygen – requiring ongoing medical care (COVID-19 related or otherwise);

Category 3: Hospitalized, not requiring supplemental oxygen – no longer requires ongoing medical care. This would include those kept in hospital for quarantine/infection control, awaiting bed in rehabilitation facility or homecare, etc.;

Category 2: Not hospitalized, but has new or increased limitation on activities and/or new or increased requirement for home oxygen over baseline, pre-COVID-19 status;

Category 1: Not hospitalized, patient is back to their baseline, pre-COVID-19 status, that is, no new or increased limitations on activities and no new or increased oxygen use compared with baseline.

As is described in the clinical MOP, specific definitions of ventilatory support for Category 6 and 5 include:

Category 6:

- Non-invasive ventilation includes: CPAP without invasive ventilation (CPAP mask or nasal cup devices)
- BiPAP

High-flow oxygen device includes:

- High Flow Nasal Cannula (HFNC): delivers heated and humidified oxygen, with a controlled fraction of inspired oxygen (FiO₂), at a flow rate of 16 L/min or greater per minute via a nasal cannula

Category 5:

Low-flow oxygen devices provide the delivery of FiO₂ at a maximum of 15 liters per minute or less and generally less than five liters per minute and include:

- Non-rebreather mask

- HHFS – high humidified face shield
- Standard nasal cannula
- Venturi mask
- High flow nasal cannula (15 L/min or less)
- Oxymizer

To determine a subject's clinical status using the ordinal scale:

- At randomization, the ordinal scale will be assessed and should reflect a subject's clinical status at the time of randomization. As there should be <24 hours between randomization and first study product administration, the ordinal scale done at randomization suffices as the Day 1 ordinal scale.
- After Day 1, collect the ordinal scale daily while hospitalized from Day 2 through Day 29 by providing the worst clinical assessment for the previous day (i.e., midnight to midnight; 00:00 – 23:59 (24-hr clock)). For example, on study Day 3 when completing the form, the worst clinical outcome measure of Day 2 is captured with the worst being death followed by ECMO, mechanical ventilation, etc. The Day 2 measurement is assessed as occurring anytime in that 24-hour period (00:00 to 23:59). For those who are discharged prior to Day 15, collect ordinal scale on follow-up Days 15, 22 and 29 by providing the worst clinical assessment for the previous 24-hour period (00:00 to 23:59).

Chronic use of home CPAP and BiPAP pre-COVID-19:

If a patient's need for CPAP or BiPAP is a new requirement since enrollment and used to treat COVID-19 (illness), a subject should be categorized as a Category 6. If CPAP is used for another indication prior to COVID-19 (e.g., non-COVID-19 indication like sleep apnea or BiPAP for COPD), this should be considered as their baseline, pre-COVID-19 medical status, and use of these devices should not be considered when categorizing patients for ACTT. Patients who require low flow supplemental oxygen are an ordinal scale category 5 even if they get CPAP at night in the hospital for chronic diagnosis of sleep apnea. Patients who require high flow supplemental oxygen or have a new requirement for CPAP or new requirement for BiPAP are an ordinal scale category 6.

It is important to capture all deaths that occur during the study as this is one of the outcomes of the study. Death is a category on the ordinal scale. If a subject dies during the study, the site will need to complete an ordinal scale assessment for the day after death. If a subject dies within the window of the final study visit (i.e., Day 29 + 6-day window), complete an ordinal scale assessment on the day after death. For more information about the data collected for the ordinal scale, see the MOP.

For more information about the data collected for the ordinal scale, see the MOP.

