3. OBJECTIVES AND ENDPOINTS

The overall objective of ACTT-4 is to evaluate the clinical efficacy and safety of baricitinib and remdesivir (Arm 1) versus dexamethasone and remdesivir (Arm 2) among hospitalized adults who have COVID-19.

| OBJECTIVES | ENDPOINTS (OUTCOME MEASURES) |
|---|---|
| Primary Objective and Endpoint | |
| To evaluate the clinical efficacy of baricitinib + remdesivir versus dexamethasone + remdesivir as assessed by the mechanical ventilation free survival by Day 29. | Proportion of subjects not meeting criteria for one of the following two ordinal scale categories at any time by Day 29 
 • Category 8: Death • Category 7: Hospitalized, on invasive mechanical ventilation or ECMO |
| Key Secondary Objective and Endpoint | |
| To evaluate the clinical efficacy of baricitinib + remdesivir versus dexamethasone + remdesivir according to clinical status (8-point ordinal scale) at Day 15. | Proportion of subjects meeting criteria for each of the 8 ordinal scale categories on Day 15 
 • Category 8: Death; • Category 7: Hospitalized, on invasive mechanical ventilation or ECMO; |

| OBJECTIVES | ENDPOINTS (OUTCOME MEASURES) |
|--|--|
| | 
 Category 6: Hospitalized, on non-invasive ventilation or high flow oxygen devices; Category 5: Hospitalized, requiring supplemental oxygen; Category 4: Hospitalized, not requiring supplemental oxygen – requiring ongoing medical care (COVID-19 related or otherwise); Category 3: Hospitalized, not requiring supplemental oxygen – no longer requires ongoing medical care; Category 2: Not hospitalized, but has new or increased limitation on activities and/or new or increased requirement for home oxygen over baseline, pre-COVID-19 status; Category 1: Not hospitalized, patient is back to their baseline, pre-COVID-19 status, that is, no new or increased limitations on activities and no new or increased oxygen use. |
| Additional Secondary Objectives and Endpoints | |

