| To evaluate the clinical efficacy of baricitinib + remdesivir versus dexamethasone + remdesivir among subjects with a baseline ordinal scale of 5 as assessed by the proportion that do not progress to ordinal scale 6, 7 or 8 at any time by Day 29. | 
Proportion of subjects not meeting criteria for one of the following ordinal scale categories at any time by Day 29
 
 Category 8: Death Category 7: Hospitalized, on invasive mechanical ventilation or ECMO Category 6: Hospitalized, on non-invasive ventilation or high flow oxygen devices |
| 
Mortality
 
 14-day mortality 28-day mortality | 
 Date of death (if applicable) |
| Time to recovery by Day 29 | 
Day of recovery is defined as the first day on which the subject satisfies one of the following three ordinal scale categories:
 
 Category 3: Hospitalized, not requiring supplemental oxygen – no longer requires ongoing medical care; Category 2: Not hospitalized, but has new or increased limitation on activities and/or new or increased requirement for home oxygen over baseline, pre-COVID-19 status; |

| OBJECTIVES | ENDPOINTS (OUTCOME MEASURES) |
|---|---|
| | 
 Category 1: Not hospitalized, patient is back to their baseline, pre-COVID-19 status, that is, no new or increased limitations on activities and no new or increased oxygen use. |
| Time to an improvement of one category and two categories from Day 1 (baseline) using ordinal scale. | Day of one and two category improvement from baseline ordinal score |
| Subject clinical status using ordinal scale at Days 3, 5, 8, 11, 15, 22, and 29. | 
 Clinical outcome assessed using ordinal scale daily while hospitalized and on Days 15, 22, and 29. |

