5.6.2 Retention

Retention of subjects is critical to the success of the trial since the primary endpoint is measured at Day 29 (+ 6-day window) and every effort should be made to retain subjects in the study. As such, after hospital discharge, subjects will be reminded of subsequent study visits and every effort will be made to accommodate the subject's schedule to facilitate follow-up within the specified visit window. To facilitate retention, follow-up visits may be conducted by phone, home visit or remote telehealth procedure as per institutional standards if in-person visits at the clinical site on Days 15 and 29 are not feasible. The Day 22 visits are by phone call or remote telehealth procedure.

However, there are many circumstances that impact a site's ability to obtain outcome information after discharge. For example, given the clinical course of COVID-19, a subject may be readmitted to another hospital after discharge and therefore be unavailable at Day 15 or Day 22. Even if a study visit is missed, every effort should be made to keep subjects in the study to monitor for safety, readmission and mortality. Subjects should not be withdrawn from the study because a site is unable to contact them for a follow-up visit.

Subjects should not be withdrawn from this trial due to terminal illness. If a subject or family is pursuing hospice or withdrawal of care, the study visits can be curtailed as needed, but these subjects (or their LARs) should be encouraged to remain in study for the Day 29 endpoint evaluation by chart review or phone call.

In addition, in ACTT-4 we will have a visit two months after randomization to assess long term efficacy and safety outcomes. This visit will be conducted by phone or remote telehealth procedure. Because of this visit, sites will need to plan for how they will contact subjects at this late time point.

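### The Day 2 ordinal-scale form looks back to 00:00 of Day 1, so respiratory support used before randomisation can be counted as progression, mainly in the baseline-category-5 secondary endpoint

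*Protocol*

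**What the plan says.** All references are to Protocol Appendix D (ACTT-4).

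- **Baseline.** Section 8.1.2.2 says that the score at randomisation "should reflect a subject's clinical status at the time of randomization", and that "the ordinal scale done at randomization suffices as the Day 1 ordinal scale".
- **In hospital.** The same section tells sites to "collect the ordinal scale daily while hospitalized from Day 2 through Day 29 by providing the worst clinical assessment for the previous day", and defines that day as 00:00 to 23:59. Its worked example has the Day 3 form covering Day 2, so the Day 2 form covers Day 1. Section 8.1.2.1 describes the window slightly differently, as the last 24-hour period.
- **Day 1.** Section 6.1.2 defines it as the day on which any study product is first given, and allows 24 hours between randomisation and first dose. Section 8.1.1 allows screening, baseline assessments and first dose on one calendar day.
- **Endpoints.** The Section 3 objective for baseline category 5 is "the proportion that do not progress to ordinal scale 6, 7 or 8 at any time by Day 29". Its outcome measure is "Proportion of subjects not meeting criteria for one of the following ordinal scale categories at any time by Day 29". The primary endpoint has the same form for categories 7 and 8: "Proportion of subjects not meeting criteria for one of the following two ordinal scale categories at any time by Day 29". Section 9.4.9 puts the category 5 endpoint third in the fixed sequence, ahead of mortality and time to recovery.
- **After discharge.** Section 8.1.2.2 says "For those who are discharged prior to Day 15, collect ordinal scale on follow-up Days 15, 22 and 29", each time for the previous 24-hour period. Section 5.6.2 foresees that "a subject may be readmitted to another hospital after discharge and therefore be unavailable at Day 15 or Day 22".

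**The concern.** The baseline is a snapshot at one moment, and the first post-baseline record is the worst value of a whole calendar day that can begin many hours earlier. No text limits the Day 1 window to the time after randomisation.

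Take a subject on high-flow oxygen at 03:00, weaned to low flow, randomised at noon in category 5 and dosed that afternoon. The Day 2 form reads category 6. Under a rule that counts category 6, 7 or 8 at any time, this subject has failed, although nothing worsened after randomisation. Such a subject is eligible, because inclusion criterion 5 requires low-flow or higher support at the time of randomisation and does not ask what was used earlier that day.

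There is also a reverse gap. If the first dose is given on the calendar day after randomisation, Day 1 starts at that midnight. The hours between randomisation and midnight are then covered neither by the snapshot nor by the Day 2 form.

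At stake is the third test in the fixed sequence. A loss of power there also closes the route to the confirmatory tests of mortality and time to recovery.

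**Working it through.** **1. Windows set side by side**

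| Case | Baseline score | Day 2 form covers | Consequence |
|---|---|---|---|
| Randomised and first dosed on the same calendar day | Status at randomisation | That day from 00:00 | Hours before randomisation are included |
| First dosed on the next calendar day | Status at randomisation | Dosing day from 00:00 | Hours from randomisation to midnight are in no form |

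In the second case, support that continues past midnight is still recorded. Only support that began and ended within those hours is lost.

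**2. The plan's own figure**

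Table 9 gives 1382 subjects for 0.85 versus 0.90, two-sided 5%, with power 80% (exact score) and 80.5% (Kaplan-Meier with Greenwood). With n = 691 per arm, mean proportion p̄ and Δ = p2 − p1:

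power = Φ{[Δ − 1.96·√(2p̄(1 − p̄)/n)] / √(p1(1 − p1)/n + p2(1 − p2)/n)}

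- Null standard error: √(2 × 0.875 × 0.125/691) = 0.01779.
- Alternative standard error: √((0.85 × 0.15 + 0.90 × 0.10)/691) = 0.01774.
- Power = Φ[(0.05 − 1.96 × 0.01779)/0.01774] = 80.3%. With the unpooled error throughout it is 80.5%.

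The plan's figure reproduces, and this point does not change it.

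**3. Sensitivity of the category 5 endpoint**

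The protocol gives no design rates for this endpoint and no misclassification rate, so the following are assumptions:

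- Share in category 5: 72%. ACTT-2 counts in Table 2 of Section 2.1.1 agree: (287 + 276)/(287 + 276 + 104 + 113) = 563/780 = 72%.
- n = 0.72 × 691 = 497.5 per arm.
- True non-progression: 0.80 versus 0.87.
- A fraction f of true non-progressors is falsely counted, equally in both arms, so each proportion p becomes p(1 − f).

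| f | Proportions | Difference | Standalone power |
|---|---|---|---|
| 0 | 0.800 vs 0.870 | 0.0700 | 84.6% |
| 0.5% | 0.796 vs 0.866 | 0.0696 | 83.5% |
| 1% | 0.792 vs 0.861 | 0.0693 | 82.4% |
| 2% | 0.784 vs 0.853 | 0.0686 | 80.2% |
| 5% | 0.760 vs 0.826 | 0.0665 | 73.6% |

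Check at f = 2%: the null standard error is 0.02445 and the alternative 0.02435, so power = Φ[(0.0686 − 1.96 × 0.02445)/0.02435] = 80.2%.

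Standalone means that the need for the first two tests to reject is ignored. The table shows sensitivity and does not estimate the actual error.

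**4. Direction**

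Status before randomisation cannot depend on allocation. False events are therefore balanced in expectation. The type I error is preserved, and the observed difference shrinks by the factor 1 − f.

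**The case against.** **Few subjects are affected, and the rates are assumed.** This stands. Under Section 8.1.2.2 a nasal cannula at 15 L/min or less is still category 5, so only flow of 16 L/min or more, or new CPAP or BiPAP, earlier on the same day matters. Subjects dosed on the next calendar day are not exposed to the false-event problem. At 0.5% to 1% the loss is 1 to 2 points of power, and nothing in the documents supports a rate as high as 5%.

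**The manual of procedures or the SAP may deal with it.** This stands only in part. The objective speaks of progression, and status before baseline is not progression. But the protocol itself fixes the window at 00:00 to 23:59, so a manual that started it at randomisation would contradict it. If the form holds one worst value for the day without times, an analysis rule cannot separate the two parts of Day 1. Dropping the Day 2 form would discard real worsening after randomisation.

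**A reader might infer that the primary endpoint is also misclassified.** The documents do not support that. A false category 7 needs invasive ventilation or ECMO that ended earlier on the day of randomisation. Subjects ventilated at randomisation are excluded, Section 8.1.2.3 expects nobody to be ventilated on Day 1, and a death cannot arise this way.

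**A reader might also infer that ventilation after discharge is never captured.** That is too strong. Section 7.4 requires every readmission to be documented, with daily ordinal scoring. The notes to the Schedule of Assessments have remote contacts ask about readmission and mortality. Days of ventilation or ECMO to Day 29 are a separate endpoint in Section 3, and Section 8.3.1 makes readmission for medical worsening an SAE. The Endpoint Review Committee in Section 9.3 may also review difficult cases. What remains is narrow: no text says how support given at a non-study hospital between contacts enters the scale.

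**Conclusion.** The point holds in a limited form. As written, Section 8.1.2.2 can record support used before randomisation as post-baseline status when randomisation and first dose share a calendar day, and leaves hours after randomisation unrecorded when they do not. The consequence falls mainly on the baseline-category-5 endpoint. It is a loss of power through dilution, balanced between arms, with no bias towards either treatment and a negligible effect on the primary endpoint.

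The size cannot be derived from the documents. Under the assumptions shown, standalone power falls from about 85% to between 84% and 74% for false-event fractions from 0.5% to 5%, and the lower fractions are the easier to defend. The written rule nevertheless yields a wrong classification for an identifiable group of eligible subjects, so this is more than missing detail. It is worth correcting because the correction costs almost nothing.

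**What to change.** State in Section 8.1.2.2 that the Day 2 form records the worst status from the time of randomisation through 23:59 of Day 1, and that this also applies when the first dose falls on the calendar day after randomisation. Bring the description of the window in Section 8.1.2.1 into line, and carry the same instruction onto the form.

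As a minor addition, when a Day 15, 22 or 29 contact reveals a readmission, especially to a non-study hospital, record the highest respiratory support since the last contact with its date, and use it for the endpoints defined at any time by Day 29.

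The cost is one sentence, a form instruction and a follow-up question at contacts that already take place. The downside is slightly more chart checking on Day 2, because sites must separate support used before randomisation from support used after it.

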8.1.2.3 National Early Warning Score (NEWS)

NEWS has demonstrated an ability to discriminate subjects at risk of poor outcomes. (Smith, 2016). This score is based on 7 clinical parameters (see [Table 5](#)). In ACTT-4, the NEWS is being used as a severity of illness scores and should be evaluated at baseline (Day 1) only. The 7 parameters can be obtained from the hospital chart or electronic medical record (EMR) using measurements taken prior to first study product administration. A numeric score is given for each parameter (e.g., a RR of 9 is one point, oxygen saturation of 92 is two points). Typically, ECMO

Appendix D - ACTT-4: Baricitinib/Remdesivir vs Dexamethasone/Remdesivir and mechanically ventilated subjects should be assigned a score of 3 for RR (RR <8) regardless of the ventilator setting. Subjects on ECMO should get a score of 3 for heart rate since they are on cardiopulmonary bypass. However, given that in ACTT-4 the NEWS is done at baseline only, no patients should be on ECMO or mechanically ventilated on Day 1.

Table 5. National Early Warning Score (NEWS)

| PHYSIOLOGICAL PARAMETERS | 3 | 2 | 1 | 0 | 1 | 2 | 3 |
|--------------------------|-------|----------|-------------|-------------|-------------|-----------|------------|
| Respiration Rate | ≤8 | | 9 - 11 | 12 - 20 | | 21 - 24 | ≥25 |
| Oxygen Saturations | ≤91 | 92 - 93 | 94 - 95 | ≥96 | | | |
| Any Supplemental Oxygen | | Yes | | No | | | |
| Temperature | ≤35.0 | | 35.1 - 36.0 | 36.1 - 38.0 | 38.1 - 39.0 | ≥39.1 | |
| Systolic BP | ≤90 | 91 - 100 | 101 - 110 | 111 - 219 | | | ≥220 |
| Heart Rate | ≤40 | | 41 - 50 | 51 - 90 | 91 - 110 | 111 - 130 | ≥131 |
| Level of Consciousness | | | | A | | | V, P, or U |

Level of consciousness = alert (A), and non-alert and arousable only to voice (V) or pain (P), and unresponsive (U).

